#### 5.5. Enrollment

The patient is considered enrolled when informed consent is obtained. Enrolled patients who do not undergo implantation with the VBX Stent Graft will be a screen failure. The principal reason for a screen failure will be recorded in the patient screening and enrollment log. Supporting documentation for all enrolled patients will be retained in site registry files.

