## 3. Registry Design

### 3.1. Description of Registry Design

This registry utilizes a prospective, multicenter, non-randomized single-arm design to collect VBX Stent Graft clinical data in its use within the indicated peripheral vasculature but outside of *de novo* iliac occlusive disease. Data will be representative of real-world, clinical use. Real world clinical use data are integral for Gore combined with data from long-term clinical investigations and reports from medical literature, to perform continuing assessments of device performance in addition to any long-term clinical investigations as well as reports in medical journals. To ensure that registry data are representative of real world use, the registry will employ broad inclusion / exclusion criteria to ensure its observational nature.

A maximum of 20 clinical registry sites (referred to as "sites" in the remainder of this document) in Europe will participate in this observational registry. Gore will maintain an updated list of all principal investigators, site names, and addresses. This list shall be kept separately from this protocol. From all enrolled patients, the first 280 implanted patients will be evaluated for the registry." No one site can contribute more than 35% of the total patient population (98 patients). There are no pathology-specific limitations at the registry or site level. The anticipated accrual rate is approximately 10 implanted patients per month for a total accrual period of approximately 28 months based upon the rapidity of site-start-up.

Patients may be enrolled into the registry provided all inclusion and no exclusion criteria are met as specified in **Section 4**. Patients will be evaluated through hospital discharge with follow-up data collection up to 5 years post-treatment. Patients will be followed according to the regimen determined by their follow-up physician with entry into an Electronic Data Capture (EDC) system. Total estimated duration of the registry is 88 months.

- 3.2. Registry Endpoint(s)
  - 3.2.1. Definitions

The definitions in

Table 1 are provided to facilitate consistent reporting across all registry sites.

Protocol Term	Definition
Procedural Success	Technical Success (successful access, delivery, accurate deployment, and withdrawal of catheters) with patent VBX Stent Graft at end of procedure
	Primary - Uninterrupted patency with no procedures performed on or at the margins of the treated segment.

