#### 5.6.1. Unsuccessful Procedure

Patients who undergo the VBX Stent Graft implant procedure but are not successful either by access failure or need for an open conversion are asked to be entered in the EDC system. EDC entry may include a description of any observed procedure or VBX Stent Graft-related AEs as well as any device deficiencies.

Investigators are advised to collect follow-up information from one clinical visit following hospital discharge to ensure that the description of any AEs associated with the device or procedure are complete.

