10.3.2. Analysis Populations

All enrolled patients meeting the inclusion / exclusion criteria and treated with the VBX Stent Graft will be included in the primary and secondary endpoint analyses.

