2.0 Study Design Overview

Primary Objective(s)

The primary objective of the VBX 17-04 registry is to collect post-market safety and performance data of the GORE[®] VIABAHN[®] VBX Balloon Expandable Endoprosthesis (VBX Stent Graft) in peripheral vessels in patients who require interventional treatment

Design Summary

This registry utilizes a prospective, multicenter, non-randomized single-arm design to collect VBX Stent Graft clinical data in its use within the peripheral vasculature but outside of *de novo* iliac occlusive disease. Data will be representative of real-world, clinical use. Combined with data from long-term clinical investigations and reports from medical literature, real world clinical use data is integral for Gore to perform continuing assessments of its performance in addition to any long-term clinical investigations as well as reports in medical journals. To ensure that registry data is representative of real world use, the registry will employ broad inclusion / exclusion criteria to ensure its observational nature.

A maximum of 20 clinical registry sites (referred to as "sites" in the remainder of this document) in Europe will participate in this observational registry. Gore will maintain an updated list of all principal investigators, site names, and addresses. This list shall be kept separately from this protocol. From all enrolled subjects the first 280 implanted patients will be evaluated for the registry." No one site can contribute more than 35% of the total patient population (98 patients). There are no pathology-specific limitations at the registry or site level. The anticipated accrual rate is approximately 10 implanted patients per month for a total accrual period of approximately 28 months based upon the rapidity of site-start-up.Study Endpoints

Study Endpoints

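### A VBX attempt that ends with no implant is a procedural failure by definition, yet the plan's most direct reading drops it from the denominator and no visible passage gives it an analysis status

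*Protocol*

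**What the plan says.** **Endpoint.** Table 1 of the protocol (3.2.1), repeated in the SAP (2.1.2), defines procedural success as "Technical Success (successful access, delivery, accurate deployment, and withdrawal of catheters) with patent VBX Stent Graft at end of procedure". It is one of the two components of the primary endpoint (Protocol 3.2.2, SAP 2.1.1).

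**Who is analysed.** Three rules bear on the denominator:

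- Protocol 5.5: "Enrolled patients who do not undergo implantation with the VBX Stent Graft will be a screen failure". It adds: "The principal reason for a screen failure will be recorded in the patient screening and enrollment log".
- Protocol 3.1: "the first 280 implanted patients will be evaluated for the registry". SAP 2.0 has the same rule: "From all enrolled subjects the first 280 implanted patients will be evaluated for the registry".
- Protocol 10.3.2, and SAP 6.0 ii in the same words: "All enrolled patients meeting the inclusion / exclusion criteria and treated with the VBX Stent Graft will be included" in the primary and secondary endpoint analyses. Neither document defines what being treated with the device means.

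**Failed attempts.** Protocol 5.6.1 covers "Patients who undergo the VBX Stent Graft implant procedure but are not successful either by access failure or need for an open conversion". Sites are asked to enter them in the EDC system and advised to collect information from one visit after discharge. On content, it says: "EDC entry may include a description of any observed procedure or VBX Stent Graft-related AEs as well as any device deficiencies". Nothing there says whether these patients enter the primary analysis or how they count.

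**The concern.** The endpoint names access and delivery as things that can fail. A patient in whom access or delivery fails, and who leaves the procedure with no VBX, cannot be among the 280 implanted and is a screen failure under 5.5. The denominator is then selected on implantation, which is itself part of the outcome being measured.

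The same patient also has two descriptions: a screen failure in 5.5 and an unsuccessful procedure in 5.6.1. No visible passage says which governs analysis.

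Two results are at stake. The procedural-success rate, and any composite built on it, may sit too high. It is also unclear whether device- or procedure-related SAEs and deaths in these patients count in the 30-day safety endpoints, although 5.6.1 and 9.1.3 provide for collecting them.

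**Working it through.** **1. Tracing the patients through the rules**

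| Outcome of the procedure | Success by Table 1? | In the denominator on the most direct reading? |
|---|---|---|
| VBX attempted, access or delivery fails, no VBX implanted | No | No: screen failure, not among the 280 implanted |
| VBX implanted but inaccurately deployed | No | Yes |
| VBX implanted but occluded at the end of the procedure | No | Yes |
| VBX implanted, then open conversion | Can count as a failure | Yes |
| First device fails, another VBX implanted | Depends on how the first failure is judged | Yes |

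Only the first row is affected. The endpoint can still record failures among implanted patients.

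**2. The plan's own precision figure**

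Input: n = 280 and a margin of error below 6% (Protocol 10.2, SAP Sample Size Calculations). The normal-approximation half-width is 1.96 × √(p(1 − p)/n).

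- p = 0.5: 1.96 × √(0.25/280) = 5.86%.
- p = 0.971, the SAP planning value for clinical success: 1.97%.

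The stated figure reproduces. The exact half-width at p = 0.5 is 6.01%, marginally above it, but that is far from the planning rates.

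**3. Effect of omitting k failed attempts**

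Let s be the successes among 280 implanted patients and r = s/280. The per-attempt rate is s/(280 + k), so the overstatement is r × k/(280 + k). It cannot be negative. For k = 1 it is 1/281 = 0.36 points at r = 100%, and 0.95 × 1/281 = 0.34 points at r = 95%.

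The documents give no k, so the values below are assumptions. Intervals are exact binomial 95%, the method named in SAP 6.0.

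| Implanted only | k | Per attempt | Overstatement |
|---|---|---|---|
| 280/280 = 100% (98.7 to 100) | 3 | 280/283 = 98.9% (96.9 to 99.8) | 1.06 points |
| 280/280 = 100% (98.7 to 100) | 5 | 280/285 = 98.2% (96.0 to 99.4) | 1.75 points |
| 266/280 = 95.0% (91.8 to 97.2) | 5 | 266/285 = 93.3% (89.8 to 95.9) | 1.67 points |

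The per-attempt point estimate first falls below the implanted-only lower limit at k = 4 when all implanted patients succeed (280/284 = 98.59% against 98.69%). At 266/280 this happens at k = 10 (266/290 = 91.72% against 91.75%). These mark scale only: they set a point estimate against an interval, and the two intervals still overlap.

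**4. How large might k be?**

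Protocol 1.1 reports 100% technical success in the pivotal study, which points to a small k. That study was in de novo iliac occlusive disease, which this registry excludes. If its n = 98 is also the technical-success denominator (an assumption), the exact upper limit for 0/98 failures is 1 − 0.025^(1/98) = 3.7%. Beside 280 implants that gives 280 × 0.0369/(1 − 0.0369) = 10.7, so k from 0 to about 10 is compatible. The upper end is a confidence limit, not an expectation.

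**5. Treatment categories**

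In a category at its cap of 50 (Protocol 4.1.1), one omitted failure shifts a 100% rate by 1/51 = 1.96 points. The exact interval for 50/50 is 92.9 to 100, which contains 50/51 = 98.0%. The point estimate moves more than in the whole registry, but the wider interval absorbs it.

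**The case against.** The strongest reply is that exclusion is never stated. Section 5.6.1 treats unsuccessful procedures as their own group, so a screen failure could mean that no implant procedure took place. The analysis population uses a different word from implanted. The 280 may be only an accrual count. Passages that might settle the matter (the registry schema, Protocol 10.1, and the SAP dataset and table specifications) are missing or incomplete in the copy reviewed. All of this stands as a limit on certainty: exclusion is inferred from passages that are not reconciled. But the alternative reading still gives these patients no analysis status, and it does not override 5.5, which makes no exception for an attempt.

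It can also be said that the consequence is small. The registry tests no hypothesis and has no pass/fail rule, and k is probably low. That stands too. However, the descriptive rate and its interval are then the main result, the error can run only one way, and a larger sample does not remove it.

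Three stronger readings are tempting, and the documents do not support them:

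- **That procedural success must come out near 100% because failures are screened out.** Several kinds of failure occur in implanted patients and stay in.
- **That failed attempts go unrecorded.** Opened devices (5.6), adverse events from enrollment (9.1.3) and device deficiencies (9.3) are all captured. The gap is in analysis, not collection.
- **That small treatment categories are badly distorted.** Three omissions in a category of 50 would shift a 100% rate by 3/53 = 5.7 points, but that share exceeds the 3.7% bound above, and 50/53 = 94.3% still lies within the interval for 50/50.

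**Conclusion.** The concern holds in a limited form and should be fixed. On the most direct reading, a VBX attempt ending with no VBX implanted leaves the procedural-success denominator although it is a failure by definition, and no visible passage assigns it elsewhere. The bias is zero or favourable to the device, at about 0.35 points per omitted failure beside 280 implants. Its actual size cannot be determined from the documents. The illustrations with k = 3 and 5 give 1 to 2 points, within the plan's 6% margin but systematic. Confidence is medium, because exclusion is inferred and the relevant schema and table specifications could not be seen.

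**What to change.** - **Protocol 10.3.2 and SAP 6.0 ii:** define the population for procedural success, and for the composite, as all consented, eligible patients in whom VBX placement was attempted. An attempt means that access for VBX delivery was attempted, or a VBX was opened or introduced. Count an attempt without an implant as a procedural failure.
- **Protocol 5.5:** limit screen failure to patients with no VBX attempt, and reconcile the section with 5.6.1.
- **Protocol 3.1 and SAP 2.0:** keep 280 implanted patients as the enrolment target and as the set for patency and durability.
- **30-day safety endpoints:** include attempted patients, using the data already collected under 5.6.1 and 9.1.3, with no added visit.
- **Reporting:** give the implanted-only rate beside the per-attempt rate, with the number of non-implantations and the reasons from the screening log.

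The cost is wording in these sections, one more analysis set and a possibly slightly less favourable rate. Deciding what counts as an attempt in a combined repair needs some judgment, so the reason should be recorded case by case. Some bias may remain if failed emergency attempts are never consented, since Protocol 5.3 allows consent after the procedure. If the analysis set is left as it is, reporting the count and reasons beside the implanted-only rate would still expose most of the problem.

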#### 5.6. Procedure

The VBX Stent Graft implant procedure will be performed according to standard practice of the enrolling institution. As stated in the IFU, implanting investigators are advised to evaluate their patient for concomitant anticoagulation and / or antiplatelet medication therapy prior to and after the procedure. The necessity and choice of antiplatelet therapy can be individualize according to patient history as well as the pathology treated.

Any used VBX Stent Graft devices (implanted or opened but not implanted) will be recorded on the device accountability electronic Case Report Form (eCRF). It is recommended that a post-deployment angiogram is performed at the end of the procedure to assess device condition and efficacy of treatment provided that the patient's renal function is not prohibitive.

Procedural complications arising after enrollment of an eligible patient will be treated per investigator's best medical judgment as well as recorded in the EDC.

#### 5.6.1. Unsuccessful Procedure

Patients who undergo the VBX Stent Graft implant procedure but are not successful either by access failure or need for an open conversion are asked to be entered in the EDC system. EDC entry may include a description of any observed procedure or VBX Stent Graft-related AEs as well as any device deficiencies.

Investigators are advised to collect follow-up information from one clinical visit following hospital discharge to ensure that the description of any AEs associated with the device or procedure are complete.

#### 5.7. Reinterventions

Investigators are asked to record any additional treatments of the original pathology or interventions on the previously-implanted stent-graft(s). Clinically significant progression of the treated disease will be noted as an AE with any reintervention on the disease or device noted as treatment in its respective eCRF form.

#### 5.8. Follow Up

It is expected that implanted patients will be followed according to the standard practice of the enrolling physician. Accordingly, the registry will facilitate the collection of data obtained from physical examinations, medication use, and imaging assessments for multiple types of imaging modalities (*e.g.,* CTA or ultrasound). For the purpose of registry reporting and eCRF organization, it is expected that most implanted patients will have a clinical follow-up visit within 1-3 months of the procedure with the next follow-up or device evaluation at approximately 9-12 months post-procedure. Thereafter follow-up will continue annually until 5 years post-procedure. The frequency of implanted patient evaluations and the imaging modality used to investigate treatment and device status is up to the discretion of the follow-up physician. In some cases (i.e. patient unable to reach the hospital) a phone follow-up can be acceptable as a visit.

### 5.8.1. Follow-Up Visit Windows

To aid in registry reporting, collected data will be organized and categorized into six visits. **Table 3** describes the range of days where collected data will be assigned to either visit type. Any evaluation of the VBX Stent Graft outside of the general reporting windows can be entered in the EDC system as an unscheduled visit.

### 5.9. Patient Withdrawal from the Registry

An implanted patient may withdraw from the registry at any time and should notify their follow-up physician in this circumstance. The investigator may also withdraw the patient from the registry at any time based on his / her medical judgment. When withdrawing the participation of a patient for any reason, the site investigator or sub-investigator records the date of discontinuation, the reason for discontinuation, and the patient's condition at the time of discontinuation on the eCRF. Patients may be considered withdrawn for any of the following:

- The VBX Stent Graft is explanted
- Death
- Voluntary withdrawal
- Investigator withdrawal

• Any other medical condition where evaluation of the VBX Stent Graft is not feasible (*e.g.*, bypassed VBX Stent Graft)

If the discontinuation is caused by the development or worsening of AEs, information on the AEs must also be recorded on the appropriate eCRF. All data generated prior to patient withdrawal will be maintained, and study data will be used as appropriate. If such withdrawal is due to problems related to the registry device safety or performance, the investigator shall ask for the patient's permission to follow his / her status / condition outside the registry

If possible, an additional evaluation of the VBX Stent Graft(s) is recommended prior to their withdrawal from the registry.

Sites are advised to provide patients with a recommendation on the long-term care and follow-up necessary for a device used in their specific pathology.

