### 3.2.3. Secondary Endpoint(s)

Selected events that are illustrative of the device's potential impact to a patient from a safety perspective, overall device function described as patency or device durability captured as device integrity are the registry's secondary endpoints. Possible endpoint events will be identified from site reports with some secondary endpoints within scope of CEC adjudication.

The secondary endpoints for the VBX 17-04 registry are the following:

- VBX Stent Graft-related death within 30 days post-treatment
- Procedural-related death within 30 days post-treatment
- Procedural-related SAE within 30 days post-treatment
- VBX Stent Graft patency (primary, primary assisted, secondary) through 30 days post-treatment
- VBX Stent Graft patency (primary, primary assisted, secondary) through five years post-treatment
- VBX Stent Graft-related SAE through five years post-treatment
- VBX Stent Graft-related death through five years post-treatment
- Loss of device integrity through five years post-treatment
- Limb salvage through five years post treatment

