## 9.1.3. Adverse Event Reporting and Coding

AEs will be reported on the appropriate eCRF and documented in the patient's permanent medical record. AE reporting will start from enrollment (when informed consent is obtained). The investigator at each site is ultimately responsible for reporting AEs to the sponsor.

The following information on each reported AE will be collected:

- Adverse event name
- Adverse event onset date
- Relationship
- Classification (serious or non-serious)
- Treatment
- Outcome
- Resolution date

AEs will be coded using the Medical Dictionary for Regulatory Activities (MedDRA).

- 9.1.4. Adverse event submission guidelines:
  - AE reporting begins once the patient is enrolled in the registry. All AEs should be reported from enrollment through registry completion / discontinuation.
  - Provide a diagnosis if possible. If unable to provide a diagnosis, report the symptoms as separate events. AEs should be reported using the full name without abbreviations or narratives.
  - AEs with an outcome status of "ongoing" should be assessed at each follow-up evaluation to determine if the event has resolved. AEs ongoing at study completion / discontinuation should be left as "ongoing" on the AE case report form.

The site principal investigator or designee must report SAEs to the registry sponsor as soon as possible after onset, observation, or first reporting of the occurrence, and in accordance with applicable national regulations. It is the responsibility of each investigator to report all SAEs to the reviewing EC, according to national regulations and EC requirements. A copy of the EC report will be forwarded to the sponsor. Source documents must be submitted upon request (*e.g.*, histopathology findings, catheter lab reports, etc.). All source documents must be blinded using only the patient's unique study identifier and forwarded to the sponsor.

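### Withdrawal after explant or bypass can end safety collection before the 30-day and five-year death, SAE and limb endpoints close

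*Protocol*

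**What the plan says.** Protocol Section 5.9 introduces its list of grounds with "Patients may be considered withdrawn for any of the following". Two entries concern the fate of the device: "The VBX Stent Graft is explanted" and "Any other medical condition where evaluation of the VBX Stent Graft is not feasible", the second with a bypassed graft as its example.

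The same section sets some safeguards. The date, the reason and the patient's condition at discontinuation go on the eCRF. Data gathered before withdrawal are kept. On the triggering event it says: "If the discontinuation is caused by the development or worsening of AEs, information on the AEs must also be recorded on the appropriate eCRF". Where the withdrawal stems from device safety or performance, the investigator must ask for "permission to follow his / her status / condition outside the registry".

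Section 9.1.4 sets the reporting window: "All AEs should be reported from enrollment through registry completion / discontinuation". AEs still open at discontinuation stay coded as ongoing. Section 9.1.5 treats death as the outcome of an AE, not as an AE, and also leaves unresolved AEs as ongoing at withdrawal.

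Section 3.2.3 includes "VBX Stent Graft-related death through five years post-treatment" and "Limb salvage through five years post treatment", device-related SAE over the same five years, and device-related death, procedure-related death and procedure-related SAE within 30 days. Under Protocol Section 10.3.5 missing data leave the denominator, and under SAP Section 6.0 v patients with missing outcomes leave the analysis.

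**The concern.** Patency and integrity of a graft cannot be assessed once it is removed or bypassed, so ending those assessments is reasonable. Death, device-related SAE and limb status belong to the patient and can be ascertained without a graft in place. Section 5.9 does not separate the two kinds of endpoint, and withdrawal ends both.

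Collection can therefore stop because the device failed, in patients who plausibly carry a higher risk of a device-related death or an amputation than the rest. The missingness is then informative, and dropping missing outcomes does not correct for it. At stake is the long-term safety picture that the registry exists to provide: device-related death may look rarer, and limb salvage better, than they are.

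**Working it through.** **1. The provisions side by side**

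| Question | Where | Answer |
|---|---|---|
| Can explant or bypass end participation? | 5.9 | Yes, at discretion |
| Is the triggering AE recorded? | 5.9 | Yes |
| Is a later AE, or the later outcome of an open AE, required? | 9.1.4, 9.1.5 | No; open AEs stay ongoing |
| Does follow-up after withdrawal enter the EDC or reach the CEC? | 5.9 | No visible route; outside the registry |
| How long do the patient-level endpoints run? | 3.2.3 | 30 days or five years |
| What happens to missing outcomes? | 10.3.5; SAP 6.0 v | Excluded |
| Would early withdrawal be flagged? | 6.3 | No; deviations cover consent, eligibility and data entry |

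**2. Two hypothetical patients**

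- A graft is explanted for infection on day 12, the patient is withdrawn that day and dies of sepsis on day 20. The infection is on file as ongoing. The fatal outcome falls after the reporting window, so neither the 30-day nor the five-year death endpoint need capture it.
- An occluded graft is bypassed, the patient is withdrawn and loses the leg six months later. The loss need not be recorded as a limb-salvage failure.

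**3. The plan's own precision figure**

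Protocol Section 10.2 states a margin of error below 6% with n = 280. The normal approximation reproduces it: 1.96 × √(0.5 × 0.5 / 280) = 5.86 points at worst. At the SAP's assumed rates it gives 1.97 points (97.1%) and 2.87 points (93.6%). This is sampling error only. It does not cover events that are never collected, so it serves here only as a yardstick.

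**4. Illustrative size**

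The documents give neither an explant or bypass rate nor an event risk afterwards. Both are assumed.

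- Working range: 280 × 0.02 = 5.6 and 280 × 0.08 = 22.4 patients withdrawn. With a later event in 10% to 30%, 5.6 × 0.10 = 0.6 and 22.4 × 0.30 = 6.7 events are missed. Over 280 patients that is 0.2 to 2.4 points.
- Wider range: let k be the number withdrawn, q their later event risk, and r = 3.6% the risk in everyone else (assumed). Events missed = kq. If the withdrawn are excluded, the understatement is k(q − r)/280. If they stay in as event-free, it is kq/280.

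| Withdrawn | k | q | Events missed | Excluded (points) | Event-free (points) |
|---|---|---|---|---|---|
| 2% | 6 | 10% | 0.6 | 0.14 | 0.21 |
| 2% | 6 | 50% | 3.0 | 0.99 | 1.07 |
| 5% | 14 | 10% | 1.4 | 0.32 | 0.50 |
| 5% | 14 | 50% | 7.0 | 2.32 | 2.50 |
| 10% | 28 | 10% | 2.8 | 0.64 | 1.00 |
| 10% | 28 | 50% | 14.0 | 4.64 | 5.00 |

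The last row is an extreme corner. Under exclusion the bias is downward only if q exceeds r, which is plausible after device failure but is not shown in the documents. The amputation part of q will not apply evenly: the visceral perfusion category alone may hold up to 140 patients (Section 4.1.1).

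**The case against.** Several stronger readings are tempting, and the documents do not support them.

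- **That these events are certainly not collected.** Section 5.9 is permissive. A patient who is kept in remains under AE reporting and annual follow-up, with phone contact acceptable in some cases (Section 5.8). The accurate statement is that the events need not be collected. Discretion does leave completeness to site habit.
- **That any device failure triggers this.** Occlusion, loss of integrity and reintervention are not listed grounds, and reinterventions are recorded (Section 5.7). Only explant and non-evaluability are listed.
- **That device-related SAEs in general, or the primary endpoint, are seriously affected.** The AE behind the withdrawal must be recorded. If it is a device-related SAE, the patient already counts, and a later SAE adds nothing to a cumulative percentage of patients affected. What remains exposed is later death, limb loss, and a first device-related SAE that follows a withdrawal for another cause.
- **That loss of one of several grafts ends follow-up of the others.** Section 5.9 does not say so. It also does not rule it out, so a clarifying sentence is enough.
- **That analysis can do nothing.** The withdrawal date and reason are captured, so these patients can be identified, counted and bounded. Bounds do not replace the missing outcomes.

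The remaining caution stands. Section 5.12 on explant procedures has no visible text, and Tables 2 and 3 and the CEC Charter are not available. A rule on follow-up after explant could sit there. Sections 5.9 and 9.1.4 would still have to agree with it. It is also true that the registry is descriptive, with no hypothesis and no pass/fail criterion.

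**Conclusion.** The concern holds in limited form. As visibly written, the plan allows a patient to leave after explant or bypass, requires no AE reporting afterwards, and gives no route by which later deaths, limb losses or first later device-related SAEs reach the endpoints. If risk is higher in those patients, device-related death is under-counted and limb salvage is overstated.

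The size is unknown. The working assumptions give from under one event to about seven. The low end is negligible for most endpoints, but for a rare one such as device-related death even one or two missed events could be a material share. The primary endpoint is probably little affected. This should be fixed, with medium confidence because of the text that cannot be seen.

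**What to change.** - **Section 5.9.** State that explant, bypass or other non-evaluability ends patency and integrity assessment of that graft only. The patient stays in the registry for SAEs, vital status, limb status and any remaining VBX grafts, by standard-of-care visit or phone contact, until five years, death or withdrawal of consent. Because withdrawal by the investigator remains on the list, add that explant or bypass alone is not a ground for it.
- **Status after withdrawal.** Where the patient gives permission for further follow-up, enter what is learned in the EDC so that it can reach the CEC and the endpoints.
- **Consistency.** Align Sections 5.9 and 9.1.4 with each other and with whatever Section 5.12 contains.
- **SAP Section 6.0 v.** For patients already withdrawn on these grounds, report their number and give best- and worst-case bounds for death and limb salvage.

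The cost is a protocol amendment with EC approval at up to 20 sites, a few extra eCRF entries, and possibly slightly less favourable safety figures. No test or treatment changes. The amendment is most useful while patients are still in follow-up, because missed events may not be recoverable later.
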